3.4.2 Exclusion Criteria

1. Prior treatment of this cancer including:
 - a. Surgery
 - b. Radiation therapy
 - c. Chemotherapy
2. Receiving any other investigational agents.
3. Prior therapy with any Cdk4 inhibitor.
4. Any of the following in the previous 6 months:
 - a. myocardial infarction
 - b. severe/unstable angina
 - c. coronary/peripheral artery bypass graft
 - d. symptomatic congestive heart failure
 - e. cerebrovascular accident
 - f. transient ischemic attack
 - g. symptomatic pulmonary embolism.
5. Uncontrolled intercurrent illness including, but not limited to:
 - a. ongoing or active infection
 - b. symptomatic congestive heart failure
 - c. unstable angina pectoris
 - d. uncontrolled symptomatic cardiac arrhythmia,
 - e. psychiatric illness/social situations that would limit compliance with study requirements.
6. Pregnant/nursing.

7. Unwilling to employ adequate contraception.
8. Known HIV-positive on combination antiretroviral therapy.

NOTE: HIV-positive patients on combination antiretroviral therapy are ineligible because of the potential for pharmacokinetic interactions with PD 0332991. In addition, these patients are at increased risk of lethal infections when treated with marrow-suppressive therapy.

9. Known metastatic disease.
10. Current use of anticoagulation therapy.
11. Previous excisional biopsy of the breast cancer or sentinel lymph node biopsy.
12. Any condition that impairs patient's ability to swallow PD 0332991 tablets (e.g., gastrointestinal tract disease resulting in an inability to take oral medication or a requirement for IV alimentation, prior surgical procedures affecting absorption)
13. History of allergic reactions attributed to compounds of similar chemical or biologic composition to PD 0332991 or other agents used in the study.
14. Corrected QT (QTc) interval >470 msec.
15. Current use or anticipated need for food or drugs that are known strong CYP3A4 inhibitors (i.e. grapefruit juice, verapamil, ketoconazole, miconazole, itraconazole, posaconazole, erythromycin, clarithromycin, telithromycin, indinavir, saquinavir, ritonavir, nelfinavir, lopinavir, atazanavir, amprenavir, fosamprenavir, nefazodone, diltiazem, and delavirdine) or inducers (i.e. dexamethasone, glucocorticoids, progesterone, rifampin, phenobarbital, St. John's wort). See Appendix H

3.5 Eligibility Criteria for the Adjuvant Cohort

3.5.1 Inclusion Criteria

1. Derived benefit from PD 0332991 in the neoadjuvant setting in this trial. This includes the 26 patients who achieved complete cell cycle arrest only after the addition of PD 0332991 (C1D1 Ki67 >2.7% and C1D15 Ki67 \leq 2.7%) from the main study (PIK3CA WT, mutant, or unknown cohorts) as well as any patients who have a Ki67 \leq 10% on C1D15 biopsy in the endocrine resistant cohort.
2. ECOG performance status of 0, 1 or 2 (Appendix A).

3. If premenopausal, patient must be willing to comply with pregnancy requirements laid out in Section 5.5.
4. Adequate organ and marrow function as defined below:
 - a. leukocytes \geq 3,000/mcL
 - b. absolute neutrophil count \geq 1,500/mcL
 - c. platelets \geq 100,000/mcL
 - d. total bilirubin \leq upper normal institutional limits
 - e. AST(SGOT)/ and ALT(SGPT) \leq 2.5 X institutional upper limit normal
 - f. Creatinine \leq upper normal institutional limits
5. Underwent surgery of the breast and axilla for curative intent.
6. At least 4 weeks post completion of adjuvant chemotherapy and radiation therapy if indicated.
7. Patients who already started on adjuvant hormonal therapy are eligible under the following conditions:
 - a. For the 26 patients who enrolled in the initial cohorts and derived benefit from neoadjuvant PD 0332991 (C1D1 Ki67 $>2.7\%$ and C1D15 Ki67 $\leq 2.7\%$), adjuvant PD 0332991 should be initiated as soon as possible if adjuvant hormonal therapy has been initiated and the patient has completed radiation if indicated.
 - b. For patients who enrolled in the endocrine resistant cohort and derived benefit from neoadjuvant PD 0332991 (C1D15 Ki67 $\leq 10\%$), adjuvant PD 0332991 should be initiated within 6 months or sooner after initiation of adjuvant hormonal therapy.
8. Able to understand and willing to sign an IRB-approved written informed consent document.

3.5.2 Exclusion Criteria

1. Any of the following in the previous 6 months:
 - a. myocardial infarction
 - b. severe/unstable angina
 - c. coronary/peripheral artery bypass graft
 - d. symptomatic congestive heart failure
 - e. cerebrovascular accident
 - f. transient ischemic attack
 - g. symptomatic pulmonary embolism.
2. Uncontrolled intercurrent illness including, but not limited to:
 - a. ongoing or active infection
 - b. symptomatic congestive heart failure

- c. unstable angina pectoris
- d. uncontrolled symptomatic cardiac arrhythmia
- e. Psychiatric illness/social situations that would limit compliance with study requirements.

3. Pregnant/nursing.
4. Unwilling to employ adequate contraception.
5. Known HIV-positive on combination antiretroviral therapy.

NOTE: HIV-positive patients on combination antiretroviral therapy are ineligible because of the potential for pharmacokinetic interactions with PD 0332991. In addition, these patients are at increased risk of lethal infections when treated with marrow-suppressive therapy.

6. Known metastatic disease.
7. Any condition that impairs patient's ability to swallow PD 0332991 tablets (e.g., gastrointestinal tract disease resulting in an inability to take oral medication or a requirement for IV alimentation, prior surgical procedures affecting absorption)
8. History of allergic reactions attributed to compounds of similar chemical or biologic composition to PD 0332991 or other agents used in the study.
9. Corrected QT (QTc) interval >470 msec.
10. Current use or anticipated need for food or drugs that are known strong CYP3A4 inhibitors (i.e. grapefruit juice, verapamil, ketoconazole, miconazole, itraconazole, posaconazole, erythromycin, clarithromycin, telithromycin, indinavir, saquinavir, ritonavir, nelfinavir, lopinavir, atazanavir, amprenavir, fosamprenavir, nefazodone, diltiazem, and delavirdine) or inducers (i.e. dexamethasone, glucocorticoids, progesterone, rifampin, phenobarbital, St. John's wort). See Appendix H

3.6 Inclusion of Women and Minorities

Women and members of all races and ethnic groups are eligible for this trial.

4.0 PRE-REGISTRATION AND REGISTRATION PROCEDURES

4.1 Pre-Registration

This subsection applies only to patients enrolling to the PIK3CA Mutant and WT cohorts. Enrollment to those cohorts is closed as of Amendment #7.

Patients will be pre-registered to the NCI 9170 trial if it is active for patient enrollment at the participating institution unless patient is not an appropriate candidate for the NCI9170 trial per treating physician. Otherwise, patients will be pre-registered through this trial using the following procedures for PIK3CA sequencing. No pre-registration is required for the Endocrine Resistant Cohort.

Patients must not start any protocol intervention prior to pre-registration through the Siteman Cancer Center. All eligible and consenting patients will be pre-registered to this protocol for the purposes of PIK3CA sequencing; if mutation is identified, the patient will then be registered to the PIK3CA Mutant Cohort if eligible for study treatment. If mutation is not identified, the patient will then be registered to the PIK3CA Wild Type Cohort if eligible for study treatment. Pre-registration is not required for patients to be enrolled in the endocrine resistant cohort, as PIK3CA mutation status will not be assessed.

The following steps must be taken:

1. Confirmation of patient pre-registration eligibility by Washington University
2. Pre-Registration of patient in the Siteman Cancer Center database
3. Assignment of unique patient number (UPN)

Once the patient has been entered in the Siteman Cancer Center database, the WUSM coordinator will forward verification of enrollment and the UPN via email.

4.1.1 Confirmation of Patient Eligibility for Pre-Registration

Confirm patient eligibility by scanning or faxing the information listed below to the research coordinator listed in the *Siteman Cancer Center Clinical Trials Core Protocol Procedures for Secondary Sites* packet and [name] ([contact]) at least one business day prior to registering patient:

1. Your name and contact information (telephone number, fax number, and email address)
2. Your site PI's name, the registering MD's name, and your institution name

3. Patient's race, sex, and DOB
4. Three letters (or two letters and a dash) for the patient's initials
5. Currently approved protocol version date
6. Copy of signed consent form (patient name may be blacked out)
7. Planned date of sample shipment
8. Completed pre-registration eligibility checklist, signed and dated by a member of the study team
9. Copy of appropriate source documentation confirming patient eligibility

4.1.2 Patient Pre-Registration in the Siteman Cancer Center Database

Registrations may be submitted Monday through Friday between 8am and 5pm CT. Urgent late afternoon or early morning enrollments should be planned in advance and coordinated with the Washington University research coordinator. Registration will be confirmed by the research coordinator or his/her delegate by email or fax within one business day. Verification of eligibility and pre-registration should be kept in the patient chart.

Patients at all sites must be pre-registered through the Siteman Cancer Center database at Washington University.

4.1.3 Assignment of UPN

Each patient will be identified with a unique patient number (UPN) for this study. Patients will also be identified by first, middle, and last initials. If the patient has no middle initial, a dash will be used on the case report forms (CRFs). All data will be recorded with this identification number on the appropriate CRFs.

4.1.4 Additional Notes

- Pre-registration tests/procedures (see Section 10.0) must be completed within the guidelines specified on the test schedule.
- At the time of IRB submission, site should request several biopsy kits by contacting the Alliance Central Specimen Bank (address and phone numbers listed in Section 9.1).
- Following pre-registration and research tumor biopsy, patient may start Cycle 0 anastrozole (and goserelin if premenopausal) according to the instructions in Section 5.1.

4.2 Registration

The information in this section applies to patients enrolling to ALL cohorts.

Patients must not start any protocol intervention prior to registration through the Siteman Cancer Center.

The following steps must be taken before registering patients to this study:

1. Confirmation of patient eligibility by Washington University
2. Registration of patient in the Siteman Cancer Center database
3. Assignment of unique patient number (UPN) if not pre-registered through this trial

Once the patient has been entered in the Siteman Cancer Center database, the WUSM coordinator will forward verification of enrollment via email.

4.2.1 Confirmation of Patient Eligibility

Confirm patient eligibility collecting the information listed below and scanning and emailing to the research coordinator listed in the *Siteman Cancer Center Clinical Trials Core Protocol Procedures for Secondary Sites* packet and [name] at [contact] at least one business day prior to registering patient:

1. Your name and contact information (telephone number, fax number, and email address)
2. Your site PI's name, the registering MD's name, and your institution name
3. Patient's race, sex, and DOB
4. Three letters (or two letters and a dash) for the patient's initials
5. Currently approved protocol version date
6. Copy of signed consent form (patient name may be blacked out)
7. Planned date of enrollment
8. Completed eligibility checklist (Appendix B), signed and dated by a member of the study team
9. Copy of appropriate source documentation confirming patient eligibility

4.2.2 Patient Registration in the Siteman Cancer Center Database

Registrations may be submitted Monday through Friday between 8am and 5pm CT. Urgent late afternoon or early morning enrollments should be planned in advance and coordinated with the Washington University research coordinator. Registration will be confirmed by the research coordinator or his/her delegate by email within one business day. Verification of eligibility and registration should be kept in the patient chart.

All patients at all sites must be registered through the Siteman Cancer Center database at Washington University.

4.2.3 Assignment of UPN

Each patient will be identified with a unique patient number (UPN) for this study. Patients will also be identified by first, middle, and last initials. If the patient has no middle initial, a dash will be used on the case report forms (CRFs). All data will be recorded with this identification number on the appropriate CRFs.

5.0 TREATMENT PLAN

5.1 Neoadjuvant Treatment

Treatment will be administered on an outpatient basis. Patients will be instructed to make use of medication diaries (Appendices D and E) to act as a records for administration of PD 0332991 and anastrozole. Appropriate dose modifications are described in Section 6.0. No investigational or commercial agents or therapies other than those described below may be administered with the intent to treat the patient's malignancy.

Cycle 0 (Only applicable for PIK3CA Mutant and WT cohorts)

Before Cycle 1 Day 1 starts, patients who enrolled in the PIK3CA mutant or WT cohort should have completed Cycle 0. Cycle 0 therapy is 28 days of anastrozole (1mg PO daily) and, if premenopausal, goserelin 3.6mg SC every 28 days.

Cycles 1-5

Treatment with PD 0332991 combined with anastrozole (and goserelin if premenopausal) is to be 4 28-day cycles followed by a fifth cycle of 10-12 days duration consisting of daily PD 0332991 and anastrozole, with the last dose of both drugs to be given the day before surgery.

REGIMENT DESCRIPTION				
Agent	Dose	Route	Schedule	Cycle Length
PD 0332991	125 mg	PO	Daily (Days 1-21)	Cycles 1-4: 28 days
Anastrozole	1 mg	PO	Daily (Days 1-28)	Cycle 5: 10-12 days
Goserelin*	3.6 mg	SC	Q28 days	Adjuvant treatment: 28 days

* only if premenopausal; although it is preferred to be given on Day 1 of each cycle, it may be administered any day of the cycle to accommodate the Q28-day cycle for goserelin.

PD 0332991 should be taken with food. Anastrozole should be taken daily with or without food.

For both PD 0332991 and anastrozole:

- If a patient misses a day's dose entirely, she must be instructed not to make it up the next day but just take her regular dose the following day.
- If a patient vomits anytime after taking a dose, she must be instructed not to make it up but to resume subsequent doses the next day as prescribed.
- If a patient inadvertently takes an extra dose during a day, she must be instructed to not take the next day's dose.

Special Considerations for Cycle 5

Cycle 5 Day 1 of PD 0332991 may be delayed by up to 3 weeks to allow ANC to recover to $\geq 1500/\text{mcL}$ and platelets to recover to $\geq 100,000/\text{mcL}$ and other treatment related AEs

to recover to \leq grade 1 as well as to accommodate surgery scheduling. Anastrozole is continued in all patients during the neoadjuvant period. Patients who receive goserelin should also continue goserelin every 28 days during the neoadjuvant period.

CBC+D is to be performed 3 days (± 1 day) prior to surgery in patients who receive Cycle 5 therapy. Treatment with PD 0332991 should be interrupted if ANC $<$ 1,000/mcL, platelets $<$ 100,000/mcL, or patients present with any \geq grade 2 treatment-related toxicities. If a patient needs to stop treatment prematurely in Cycle 5, she will have surgery on the scheduled date unless contraindicated, as the recovery of neutropenia is usually prompt after stopping PD 0332991 due to its mechanisms of action (investigator brochure). However, surgery may be rescheduled at the discretion of the treating physician and the study chair. Patients should continue with anastrozole until the day before surgery regardless of whether they complete Cycle 5 of PD 0332991.

Patients whose ANC and/or platelets do not recover within 3 weeks following the completion of Cycle 4 will proceed to surgery as planned (3 to 5 weeks following the last dose of PD 0332991 (Cycle 4 Day 21)). For these patients, anastrozole is to be continued until the day of surgery, with the last dose of anastrozole given the day before surgery.

5.2 Surgery

Standard surgery (breast and axillary lymph node surgery) will be performed per institutional standards 2-4 weeks following the completion (Day 28) of Cycle 4 in those who did not receive Cycle 5. In patients who receive Cycle 5, surgery occurs on Day 11, 12, or 13 of Cycle 5.

Note that tissue collection is mandatory at the time of surgery for all patients.

5.3 Post Surgery Therapy

Standard adjuvant treatment, including chemotherapy, hormonal therapy, and radiation if needed, are recommended after surgery at the discretion of the treating physician.

Patients who derived benefit from the combination therapy have the option of taking PD 0332991 in combination with anastrozole for 23 cycles after surgery and adjuvant chemotherapy and radiation if indicated. Patients are determined to have derived benefit if their Ki67 is $\leq 10\%$ on C1D15 tumor biopsy if they are enrolled to the endocrine resistant cohort (including patients who enrolled prior to activation of Amendment #7) **OR** if they are among the 26 patients who enrolled initially to the main trial who required PD 0332991 to achieve complete cell cycle arrest.

PD 0332991 should be re-started at least 4 weeks after the completion of chemotherapy and radiation therapy if these treatments were planned. Hormonal therapy may be started earlier (during radiation therapy) if desired.

Anastrozole is preferred in this trial to combine with PD 0332991 in the adjuvant setting

as this is the same regimen used in the neoadjuvant setting, but alternative hormonal therapy such as another aromatase inhibitor or tamoxifen is allowed if patient could not tolerate adjuvant anastrozole. Goserelin should be administered if aromatase inhibitor is used in patients who are pre-menopausal determined by institutional standard.

After completion of adjuvant PD 0332991, patients should continue standard of care hormonal therapy (for example, anastrozole) to complete at least 5 years of adjuvant hormonal therapy. Further therapy after that is at the discretion of the treating physician.

5.4 General Concomitant Medication and Supportive Care Guidelines

While taking PD 0332991, patients should be instructed to avoid food or drugs that are known strong CYP3A4 inhibitors or inducers. Please refer to Appendix H for a list of prohibited medications.

No specific antidotes exist for the treatment of PD 0332991 overdose. Since renal excretion of PD 0332991 is minimal, the benefit of hemodialysis in the treatment of a PD 0332991 overdose is probably negligible. The treatment of overdose of PD 0332991 should consist of general supportive measures. If indicated, elimination of unabsorbed drug should be achieved by emesis or gastric lavage.

No prophylactic medications are required prior to administration of anastrozole or goserelin.

5.5 Women of Childbearing Potential

Women of childbearing potential (defined as women with regular menses, women with amenorrhea, women with irregular cycles, women using a contraceptive method that precludes withdrawal bleeding, and women who have had a tubal ligation) are required to have a negative serum pregnancy test within 7 days prior to the first dose of the study agent.

Women of childbearing potential are required to use two forms of acceptable contraception, including one barrier method, during participation in the study and for 90 days following the last dose of PD 0332991.

If a patient is suspected to be pregnant, all study drugs should be immediately discontinued. In addition a positive urine test must be confirmed by a serum pregnancy test. If it is confirmed that the patient is not pregnant, she may resume dosing.

5.6 Duration of Therapy

If at any time the constraints of this protocol are considered to be detrimental to the patient's health and/or the patient no longer wishes to continue protocol therapy, the protocol therapy should be discontinued and the reason(s) for discontinuation documented in the case report forms.

In the absence of treatment delays due to adverse events, neoadjuvant treatment may continue for 4 cycles plus the fifth short cycle or one of the following criteria applies:

- Documented and confirmed disease progression or Ki67>10 % on C1D15
- Death
- Adverse event(s) that, in the judgment of the investigator, may cause severe or permanent harm or which rule out continuation of study drug
- General or specific changes in the patient's condition render the patient unacceptable for further treatment in the judgment of the investigator
- Suspected pregnancy
- Serious non-compliance with the study protocol
- Lost to follow-up
- Patient withdraws consent
- Investigator removes the patient from study
- The Siteman Cancer Center decides to close the study

Adjuvant treatment (in patients eligible to receive it) may continue for up to 23 cycles or until one of the following criteria applies:

- Documented and confirmed disease progression
- Death
- Adverse event(s) that, in the judgment of the investigator, may cause severe or permanent harm or which rule out continuation of study drug
- General or specific changes in the patient's condition render the patient unacceptable for further treatment in the judgment of the investigator
- Suspected pregnancy
- Serious non-compliance with the study protocol (missing 50% dosing in any cycle due to non-compliance or missing study required procedures due to non-compliance determined by site investigator)
- Lost to follow-up
- Patient withdraws consent
- Investigator removes the patient from study
- The Siteman Cancer Center decides to close the study

Patients who prematurely discontinue treatment for any reason will be followed as indicated in the study calendar.

5.7 Treatment/Follow-up Decision Tree

Any patient who registers on study and then withdraws her consent prior to receiving any PD 0332991 will be considered a cancellation. No further follow-up is required. Future treatment is at the discretion of their treating physician.

If a patient is found not to have fulfilled all the eligibility requirements after starting PD 0332991, she will be removed from study treatment. All study forms up to the point of study treatment discontinuation are to be submitted. These patients will be observed for

AEs for 30 days following the last dose of PD 0332991 or the resolution of AEs at least possibly related to PD 0332991, whichever comes later. Future treatment is at the discretion of the treating physician. No further follow-up is required.

All patients except for those who withdrew consent for follow up or who refused to undergo surgery will be followed for 30 days after surgery, then yearly to document recurrence and survival status for 5 years or until recurrence whichever comes first (see Section 10.3).

Patients who received adjuvant PD 0332991 will be followed as described in Section 10.3 during adjuvant PD 0332991 therapy, then yearly following completion of PD 0332991 to complete a total of 5 years of follow-up post surgery. Should a patient discontinue adjuvant PD 0332991 early, she would be followed annually following the completion of PD 0332991 to get as close as possible to 5 years of post-surgery follow-up.

If protocol therapy was discontinued due to Ki67 > 10% on C1D15 or estradiol level in the premenopausal range in patients on goserelin, or discontinued PD 0332991 prior to completion of planned duration of therapy, the patient will be observed for AEs for 30 days following the last dose of PD 0332991 or the resolution of AEs at least possibly related to PD 0332991, then yearly to complete 5 years of follow up after surgery or until recurrence (whichever comes first). Neoadjuvant chemotherapy per physician choice is recommended before surgery. Pathologic response will be documented.

If there is physical evidence for clinical progression with bi-dimensional tape, ruler, or caliper tumor measurements of the primary tumor, a mammogram and/or ultrasound of the breast should be done to confirm/rule out progressive disease. If there is physical evidence for clinical progression with clinical assessment of the lymph node mass, an ultrasound of the axilla should be done to confirm/rule out progressive disease.

If progression is confirmed by ultrasound **OR** mammographic imaging, discontinue the study drug and operate as soon as possible or begin other anti-neoplastic approaches such as chemotherapy or radiation therapy at the treating physician's discretion. NOTE: Other anti-neoplastic approaches such as chemotherapy or radiation must not be administered while the patient is taking study drug.

For these patients:

- Obtain the serum and plasma samples (can be obtained at surgery)
- Obtain core biopsies (two frozen in OCT and two formalin-fixed) before the patient receives non-protocol chemotherapy (could be obtained at surgery)
- Complete case report form indicating whether the patient will go to immediate surgery or begin other anti-neoplastic approaches such as chemotherapy or radiation therapy. If patient goes to immediate surgery, complete surgery and pathology case report forms.
- Follow-up for 30 days following the last dose of PD 0332991 or the resolution of AEs at least possibly related to PD 0332991, then yearly to complete 5 years of followup after surgery or until recurrence (whichever comes first).

If disease progression is not confirmed by ultrasound or mammographic imaging, study drug may be continued at the investigator's discretion, and the protocol followed as described. These patients are not eligible for adjuvant PD 0332991 therapy.

Clinical progression outside the primary site (i.e., the development of a new breast mass or the development of clinical suspicion for advanced disease) should lead to further imaging evaluation and if confirmed, study drug will be discontinued. Optional tumor biopsy and blood will be obtained prior to the subsequent neoadjuvant therapy or at the time of surgery if surgery is the next step. Subsequent management is at the investigator's discretion. The patient will go off study.

Patients in whom surgery is not performed will be observed for 30-60 days after last dose of study drug and will not undergo annual follow-up.

If a patient is found to be pregnant, the study drug will be discontinued immediately. The patient will be followed for adverse events through the end of this pregnancy. Future treatment decisions are at the discretion of the patient's treating physician.

If a patient withdraws consent at any point in this study, all study data should be submitted up to the point of consent withdrawal.

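### Section 5.7 read literally recommends chemotherapy before surgery for women who stop in Cycle 5, whom 5.1 and 6.4 send to surgery, and 15.5 does not say how pCR and PEPI 0 read after chemotherapy count

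*Combined protocol and SAP*

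**What the plan says.** Section 5.7 has one paragraph covering three groups: C1D15 Ki67 above 10%, estradiol in the premenopausal range on goserelin, and women who stopped early, worded as "or discontinued PD 0332991 prior to completion of planned duration of therapy". The paragraph then states, without exception, "Neoadjuvant chemotherapy per physician choice is recommended before surgery". Progression, ineligibility and pregnancy have their own paragraphs.

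Section 5.6 describes the length of treatment: absent delays for adverse events, "neoadjuvant treatment may continue for 4 cycles plus the fifth short cycle". It adds: "Patients who prematurely discontinue treatment for any reason will be followed as indicated in the study calendar".

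The Cycle 5 text in section 5.1 gives a different route. For a stop within the cycle: "If a patient needs to stop treatment prematurely in Cycle 5, she will have surgery on the scheduled date unless contraindicated". On endocrine therapy: "Patients should continue with anastrozole until the day before surgery regardless of whether they complete Cycle 5 of PD 0332991". For women who cannot start the cycle: "Patients whose ANC and/or platelets do not recover within 3 weeks following the completion of Cycle 4 will proceed to surgery as planned". Section 5.2 times surgery at "2-4 weeks following the completion (Day 28) of Cycle 4 in those who did not receive Cycle 5". Section 6.4 says that a woman not recovered after a 3-week delay stops PD 0332991 permanently and goes to surgery 3 to 5 weeks after her last dose if possible. Footnote B of calendar 10.2 gives the same interval.

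Secondary objectives 5 and 6 ask for the PEPI 0 and pCR rates of study drug therapy. Section 15.5 promises those two rates with 90% confidence intervals but states no denominator. It does state one for clinical and radiologic response. It compares cell cycle arrest at C1D1, C1D15 and surgery by McNemar tests. It has no rule for chemotherapy given before surgery. Exploratory objective 4 deals with pathology after chemotherapy, but only for women with C1D15 Ki67 above 10%.

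**The concern.** A woman who stops PD 0332991 a few days into Cycle 5 meets the third condition in 5.7 and also the Cycle 5 rule in 5.1. One points to chemotherapy first, the other to surgery on the booked date with anastrozole continued. At stake are consistent treatment before surgery and the meaning of the surgical endpoints. A pCR after chemotherapy is not a result of study drug therapy. PEPI was developed on tumors removed after neoadjuvant endocrine therapy (1.9.6), so a score after chemotherapy measures something else. Surgical Ki67 is collected partly to learn whether cell cycle arrest reverses off drug (2.0), and chemotherapy in between obscures that reading. With no rule in 15.5, the choice would be made once the results are known.

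**Working it through.** **1. Do the surgery rules agree with each other?** Section 5.2 counts from Cycle 4 Day 28; 5.1, 6.4 and footnote B count from the last dose on Cycle 4 Day 21.

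- Gap: (28 − 21)/7 = 1 week.
- 5.2 restated from Day 21: 1 + 2 = 3 weeks to 1 + 4 = 5 weeks.

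This reproduces the 3 to 5 weeks in the other three places. The four agree, and 5.7 is the outlier.

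**2. Who is caught by 5.7?**

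- *Stops during Cycle 5.* Section 5.6 includes the short fifth cycle, so this woman has not completed the planned duration. 5.7 recommends chemotherapy; 5.1 directs surgery. The conflict is direct.
- *Never starts Cycle 5.* Section 6.4 describes her as permanently discontinued, which fits 5.7. But schema footnote 5 and footnote T of 10.2 make Cycle 5 conditional on recovery, and 12.1 treats the end of Cycle 4 as completion of neoadjuvant therapy. She can fairly be read as having completed what was planned. The conflict is possible but not certain.

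**3. Which analyses are open?** The primary endpoint is read on C1D15, before any such chemotherapy. Section 12.1 ties clinical and radiologic response to the end of Cycle 4. That leaves pCR, PEPI 0 and surgical Ki67.

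**4. Size for pCR.** Inputs from the documents: 37 women in the endocrine resistant cohort (15.3); pCR of 1.8 to 6% after chemotherapy and no more than 1% after an aromatase inhibitor (1.1). No early-stop rate is given. I assume 5 to 15%, and that every such woman receives chemotherapy.

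- Women affected: 0.05 × 37 = 1.85 to 0.15 × 37 = 5.55, about 2 to 6.
- Excess expected pCRs = women × (chemotherapy pCR − 1%): 2 × (0.018 − 0.01) = 0.016 to 6 × (0.06 − 0.01) = 0.30.
- As a share of 37: 0.016/37 = 0.04 to 0.30/37 = 0.81 percentage points.

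If 20% had chemotherapy and its pCR were 6%, the rate would be 0.8 × 1% + 0.2 × 6% = 2.0%, an excess of 1 point. Women with C1D15 Ki67 above 10% who receive chemotherapy add to the total; each contributes at most (0.06 − 0.01)/37 = 0.14 points. Their number is not stated.

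**5. Size for PEPI 0 and surgical Ki67.** The documents give no rate of either after chemotherapy, so no bias can be estimated. One woman classified the other way moves a rate by 1/37 = 2.7 points.

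**The case against.** The strongest reply is that a careful site would not be misled. Section 5.7 only recommends, at the physician's choice. Section 5.1 is directive, deals specifically with Cycle 5, and allows rescheduling only at the discretion of the treating physician and study chair. A site that cancelled imminent surgery to give chemotherapy, without a contraindication or that discretion, would depart from 5.1. Section 2.0 also expects most patients to complete Cycle 5. This stands and makes divergent treatment unlikely, but it does not limit the wording of 5.7 or supply the missing rule in 15.5.

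The conditional nature of Cycle 5 also stands. It weakens the never-started case without touching the stopped-during-cycle case.

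A reader might infer that 5.7 also contradicts the plan for C1D15 Ki67 above 10% by naming chemotherapy alone. The documents do not support this: 1.9.1 and 9.3.1 offer surgery or chemotherapy, footnote G of 10.2 leaves treatment to the physician, and a recommendation of one option is compatible with both.

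A reader might also infer that chemotherapy before surgery goes unrecorded. Section 11.0 lists form names rather than fields, so the documents cannot show that.

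Finally, objectives 5 and 6 already name study drug therapy as the target. That fixes the aim but does not say how a woman who had chemotherapy first is counted.

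**Conclusion.** The point holds in limited form. The wording of 5.7 conflicts with the Cycle 5 rules, clearly for a stop during that cycle and arguably for a woman who never starts it. The more specific directive in 5.1 softens the conflict. Separately, 15.5 leaves open how pCR, PEPI 0 and surgical Ki67 obtained after chemotherapy are counted. That gap exists even if every site follows 5.1, because chemotherapy is an accepted option after a C1D15 Ki67 above 10%.

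The estimated pCR effect is below 1 percentage point and rests on the assumed stop rates and on universal chemotherapy in that group. For PEPI 0 and surgical Ki67 the size is unknown. It would be wrong to read this as a threat to the primary result or to either design: both decision rules use C1D15 Ki67 only.

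**What to change.** **Section 5.7.** Exempt women who have had four cycles and then stop, or do not start, Cycle 5, and refer them to 5.1 and 6.4: surgery as scheduled, anastrozole continued. Optionally, word the Ki67 above 10% route as in 9.3.1.

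**Section 15.5.** Keep women given chemotherapy before surgery in the pCR and PEPI 0 denominators, counted as not achieving the endpoint on study therapy. Treat their post-chemotherapy surgical Ki67 as not evaluable in every surgical Ki67 analysis: McNemar, percent change and trajectory. Report how many there are.

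It may be tempting to count them as not arrested at surgery as well. That would enter failures never observed on study therapy. With 2 to 6 such women it could overstate loss of arrest after C1D15 by up to 2/37 = 5.4 to 6/37 = 16.2 points, in the comparison meant to address reversibility.

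**Cost.** One wording amendment, with no extra visits or patients. The pCR and PEPI 0 rates fall by 2.7 points for each such woman who would otherwise have counted as a success. The surgical Ki67 analyses lose her pair, about 2 to 6 pairs among early stoppers under the assumed rates, plus any woman with C1D15 Ki67 above 10% who has chemotherapy.
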